While there is no precedent clinical data implicating association between and important AEs such as Major Adverse Cardiovascular Events (MACE) and Suicidal Ideation and Behaviour (SIB), these AEshave been associated with biological entities targeting PsO and other Total disease indications. In the interest of ensuring subject safety, these important AEs are to be evaluated throughout the BI 730357 clinical development program, and trial subjects will be proactively screened for SIB in accordance with available regulatory guidance. Thus far no AEs consistent with MACE or SIB have been identified in the clinical program.

Even though gastritis development is not expected in humans, AE consistent with gastric intolerance or gastritis are designated as AE of special interest (AESI), to ensure timely characterization, monitoring and reporting of any such effects in this study (see Section 5.2.6.1).

Patients with PsO receiving BI 730357 may experience improvement in disease severity. However, this is a newly-developed drug at an early stage of testing, therefore an individual benefit for patients cannot be guaranteed. Nonetheless, the results from toxicity and safety pharmacology studies demonstrated an acceptable profile for clinical trials with daily oral administration. The potential risks which are described above will be minimized by close monitoring and the involvement of a DMC evaluation. These risks are considered manageable and outweighed by the potential benefits of the study drug.

As with other immunomodulatory treatments, BI 730357 may potentially increase the risk of infections in patients participating in clinical trials. Therefore, risk mitigation measures (e.g., exclusion of patients with increased risk of infections, close monitoring of adverse events, provision of guidance pertaining to treatment and management of acute infections occurring during the trial) have been included. Any patient with suspected or diagnosed COVID-19 infection should be treated according to standard of care, and interruption of trial medication should be considered.

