Patients with the targeted BI 730357 indications may be at greater risk of cardiovascular disease and associated risk factors, comorbidities in which the likelihood of severe illness from COVID-19 may be increased. Patients with evidence of a current or previous disease or medical condition (other than the target indication) that is clinically significant in the opinion of the investigator are excluded from participation in all trials with BI 730357. To prioritize the safety of patients, in areas with significant COVID-19 morbidity, remote visits will be permitted as needed to replace onsite patient visits in these trials. To ensure that patients may safely continue to participate in the clinical trial, remote visits will require, at a minimum, investigator assessment of new and ongoing adverse events, concomitant therapies, and patient compliance with the trial protocol and

Page 24 of 84

study drug. The BI trial team will remain in close contact with the investigator during the execution of a remote visit.

Trial conduct and protocol-defined procedures do not impose additional risk to trial participants. To address potential risks associated with operational aspects related to the participation in clinical trials in the context of the COVID-19 pandemic, different risk mitigation measures are considered, based on local requirements and development of the pandemic.

Recruitment of clinical trials will proceed when it is considered safe to do so in accordance with local public health guidance.

c22181693-04 Clinical Trial Protocol Page 25 of 84

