6. GENERAL ANALYSIS DEFINITIONS

6.1 TREATMENT(S)

All patients need to complete the preceding Phase II psoriasis Trial 1407-0030 and meet entry criteria for this study.

Two groups of patients are to be entered into this trial, including up to (approximately) 180 patients entered in the original trial 1407-0030 protocol (now Part 1) and approximately 90 patients entered in an extended dose-ranging segment, now Part 2 of the amended trial 1407-0030 protocol. Actual numbers of subjects entering the extension trial are to be determined by response in the preceding study.

In the first group (Part 1), patients will be considered eligible to participate in this long-term extension trial upon completing the trial 1407-0030 Week 24 end-of-treatment visit with a \geq PASI50 response. BI 730357 dose levels of up to 200 mg *q.d.* are to be administered under fasting conditions to patients in this group, reflecting the dose levels evaluated during Part 1 of trial 1407-0030.

- Patients entering the extension trial will remain on their blinded BI 730357 dose treatment from the preceding trial until the open label period of 1407-0005 begins at Visit 2/Week 12.
- At Visit 2/Week 12, patients presently assigned to double blind treatment of placebo, 25 mg, 50 mg, and 100 mg will be reassigned to the 100 mg open label dose, and patients presently assigned to the double blind treatment of 200 mg will be reassigned to 200 mg open label dose.

In the second patient group (Part 2), patients will be considered eligible to participate in this trial upon completing the trial 1407-0030 Week 12 end-of-treatment visit with a \geq PASI50 response or perceived patient improvement, at the discretion of the Investigator. Patients are to be considered eligible only if also without ongoing AEs consistent with intolerance of trial medication (including gastric intolerance) that in the opinion of the investigator would compromise the safety of the patient.

.

- All patients entering the extension trial are to be assigned at Visit 1 to receive open-label treatment with 400 mg *q.d.* (fed), the anticipated therapeutic BI 730357 dose.

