It is expected that Visit 1 of trial 1407-0005 will be performed on the same day of the EOT Visit of trial 1407-0030 in both patient groups. In the event that patients completing Part 2 of trial 1407-0030 are not able to be entered immediately into the extension trial due to administrative reasons (e.g., pending protocol approval, availability of trial medication), Visit 1 of the extension trial may be delayed for no more than 16 weeks.

The treatment period in this trial will be approximately 6 years.

Figure 6.1: 1

Trial 1407-0005 dose assignment/reassignment for patients entering from Part 1 of trial 1407-0030

[figure not shown]
[figure not shown]

Figure 6.1: 2

Trial 1407-0005 dose assignment for patients entering from Part 2 and continuing from Part 1 of trial 1407-0030

Dose selection at Week 12 is based on the safety and tolerability data from the SRD Trial 1407.1 and the MRD Trial 1407-0002, and will be contingent on DMC evaluation of all available data from Phase II trial 1407-0030. For patients entering from Part 1 of trial 1407-0030, if an unacceptable risk regarding the safety of the 200 mg dose level is reported by the DMC, the open label BI 730357 dose assignments beginning at Week 12, is to be altered to assign all patients to the 100 mg *q.d.* dose group.

All patients entering from Part 2 of trial 1407-0030 are to receive the 400 mg *q.d.* dose, as long as no unacceptable risks are identified during Part 2 of trial 1407-0030. Once Part 2 patients begin enrolling in this trial, existing patients receiving 100 mg *q.d.* in this trial will be given the option to titrate up to the 200 g *q.d.* dose, if the investigator determines that the Patients may benefit from the higher dose.

The first Part 2 patients enrolled in this study on December 10, 2020 and at that time all Part 1 patients had been in the study more than 12 weeks and had titrated to 100 mg *q.d.*

Subjects will be analyzed according to the treatment to which they were treated. The following study periods based on actual start and stop dates of study treatment administration are defined as follow.

Table 6.1: 1 Definition of Treatment Periods

Analysing Treatment Period	Start Date	Stop Date
Screening [#]	NA	NA
On-treatment*	Date/Time of the first administration of trial treatment	Date of the last administration of trial treatment + REP
Follow-up	Date of the last administration of trial treatment + REP+1 day	Date of the last per protocol visit

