- If AE onset date \leq date of End of Treatment visit in the preceding trial (1407-0030) < AE worsening date < date of first intake after week 12 re-assignment, then the AE is assigned to “first 12 weeks of treatment”.

If an AE worsening occurs on the day of week 12 visit, actual time between AE onset and study medication taken will be compared to determine AE time period (first 12 weeks, second treatment period).

If the subject discontinues before the day of week 12 visit, date of first intake after week 12 re-assignment will be missing, the AE worsening will still be assigned to “first 12 weeks of treatment”.

- If date of first intake after week 12 re-assignment \leq AE worsening date \leq date of last intake + 7 days, then the AE is assigned to “second treatment period”.

For patients who rolled over from Part 1 of the 1407-0030 trial if the onset date of an AE occurs prior to Week 12 and continues beyond Week 12 with a worsening RCTC grade after Week 12 then the AE will be captured as a TEAE both during the first 12-week period of 1407-0005 (as a new-onset TEAE) and during the second treatment period (beyond Week 12, as a worsening-TEAE).

Because there is no scheduled titration for patients who rolled over from Part 2 of trial 1407-0030 adverse events will only be summarized for the entire treatment period and will not be summarized for the first 12 weeks and after 12 weeks for these patients.

Due to differing doses, differing titration schedules and different timeframe for entering this study between patients from part 1 and part 2 of trial 1407_00030, several sets of adverse event analyses, each consisting of 11 summaries, will be presented:

- Events up to 12 weeks for patients who rolled over from Part 1 of trial 1407_00030 with treatment columns BI 25 mg, BI 50 mg, BI 100 mg and BI 200 mg
- Events after 12 weeks for patients who rolled over from Part 1 of trial 1407_00030

with treatment columns BI 25 mg/BI 100 mg, BI 50 mg/BI 100 mg, BI 100 mg/BI 100 mg and BI 200 mg/ BI 200mg.

- All events for patients who rolled over from Part 2 of trial 1407-0030 with treatment column BI 400 mg
- All events from all patients who rolled over from trial 1407-0030 (part 1 and part 2 combined) where events are classified under the treatment at onset in 1407-0005 with treatment columns BI 25 mg, BI 50 mg, BI 100 mg, BI 200 mg and BI 400 mg

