6.7 BASELINE, TIME WINDOWS AND CALCULATED VISITS

For all analyses, baseline refers to the baseline value in the 1407-0030 study.

For laboratory safety measurements, the last measurements taken prior to the intake of BI 730357 or placebo will be considered as baseline.

In general, measurements reported with a date only (and no time) and taken on the day of first administration of trial treatment will also be considered pre-treatment values.

The visit schedule with accompanying details can be found in Flow Chart in the CTP. Measurements taken after start of treatment will be considered either on- or off-treatment values based on definition in [Table 6.1: 1](#).

On-treatment measurements for EOT and EOS visit for early discontinued patients will be allocated to visits by means of time windows with the limit between adjacent windows half-way between the planned dates for the visits; the middle day is counted to the window of the later visit. Mutually exclusive relative day windows are defined below to provide derived visits that correspond to the post-baseline time points. For example, Visit 2 is planned on Day 84 and Visit 3 is planned on Day 168. Therefore, the window of Visit 2 reaches until Day 125 while the window of Visit 3 starts on Day 126. The visit schedule with corresponding windows is given in the following table.

Table 6.7: 1 Time windows for patient visits

Window No.	Window label	Nominal visit	Nominal day	Interval
1	Day 1	Visit 1	1	N/A
2	Week 12	Visit 2	84	[2, 125]
3	Week 24	Visit 3	168	[126, 209]
4	Week 36	Visit 4	252	[210, 293]
5	Week 48	Visit 5	336	[294, 377]
6	Week 60	Visit 6	420	[378, 461]
7	Week 72	Visit 7	504	[462, 545]
8	Week 84	Visit 8	588	[546, 629]
9	Week 96	Visit 9	672	[630, 713]
10	Week 108	Visit 10	756	[714, 797]
11	Week 120	Visit 11	840	[798, 881]
12	Week 132	Visit 12	924	[882, 965]
13	Week 144	Visit 13	1008	[966, 1049]
14	Week 156	Visit 14	1092	[1050, 1133]
15	Week 168	Visit 15	1176	[1134, 1217]
16	Week 180	Visit 16	1260	[1218, 1301]
17	Week 192	Visit 17	1344	[1302, 1385]
18	Week 204	Visit 18	1428	[1386, 1469]
19	Week 216	Visit 19	1512	[1470, 1553]
20	Week 228	Visit 20	1596	[1554, 1637]
21	Week 240	Visit 21	1680	[1638, 1721]
23	Week 252	Visit 22	1764	[1722, 1805]
24	Week 264	Visit 23	1848	[1806, 1889]
25	Week 276	Visit 24	1932	[1890, 1973]
26	Week 288	EOT	2016	[1974, 2029]
27	Week 292	EOS	2044	[2030, ∞]

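### In the combined dose-at-onset adverse event tables, 25/50 mg and 400 mg exposure share no calendar time, so COVID-19 cases could make the aggregate infection rates resemble a dose effect.

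*SAP*

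**What the plan says.** SAP 6.1 lists several sets of adverse event summaries. The first three keep the two source populations apart: Part 1 up to Week 12, Part 1 after Week 12, and Part 2. The last covers "All events from all patients who rolled over from trial 1407-0030 (part 1 and part 2 combined) where events are classified" by the dose being taken when they began, with five dose columns from 25 to 400 mg. SAP 6.1 adds exposure-adjusted incidence rates to the dose-at-onset set because exposure to the doses varies in length. It calls this the fifth set although only four are listed. SAP 7.8.1 describes the same analysis as an addition.

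Four statements in SAP 6.1 fix the calendar:

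- At Visit 2/Week 12, Part 1 patients on placebo, 25, 50 or 100 mg "will be reassigned to the 100 mg open label dose".
- "All patients entering from Part 2 of trial 1407-0030 are to receive the 400 mg" dose, assigned at Visit 1.
- The start of Part 2 entry is dated: "The first Part 2 patients enrolled in this study on December 10, 2020".
- The position of Part 1 on that date is also given; by then, according to the SAP, "all Part 1 patients had been in the study more than 12 weeks and had titrated to 100 mg".

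On infection, Protocol 1.4 says that "BI 730357 may potentially increase the risk of infections in patients participating in clinical trials". Severe infections are an AESI (Protocol 5.2.6.1.4), and SAP Table 7.8.1: 1 groups all events in the infections SOC of RCTC grade 3 or higher. Protocol version 4.0, of 06 October 2020, treats the pandemic as current; for example, "in areas with significant COVID-19 morbidity, remote visits will be permitted as needed to replace onsite patient visits". The SAP is dated 03 March 2021. Its visible text does not mention COVID-19 and gives no calendar-period rule for adverse events.

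**The concern.** This is the only planned adverse event set that places all five doses next to each other, and its layout invites a reading from low to high dose. Protocol 5.2.6.1.6 itself lists an indication of dose-response among the arguments for a causal relationship.

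The lowest doses and the highest dose were given in different calendar periods. If COVID-19 was more frequent in the later period, rows that include it would be higher at 400 mg for a reason unrelated to dose. The outcome most exposed is infection, the risk that the protocol names for this mechanism, at the dose that the protocol calls the anticipated therapeutic one. The error could also run the other way: a real rise in infections at 400 mg could be put down to the pandemic because the aggregate rows do not separate the two.

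**Working it through.** The documents state no infection rate, event count or power on this point, so there is no plan figure to reproduce.

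**1. Calendar overlap.** SAP 6.7 states that "Visit 2 is planned on Day 84". Counting 84 days back from 10 December 2020 gives 17 September 2020. For every Part 1 patient to be past 12 weeks on 10 December, each must have entered before 17 September, so 25/50 mg dosing was over by 10 December. Only Part 2 patients receive 400 mg, and none enrolled before that date. The calendar overlap of 25/50 mg with 400 mg dosing is therefore zero. Time on 100 and 200 mg can lie on both sides.

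**2. Amount of exposure.** Using the planned maximum numbers in the synopsis, patient-years = patients × weeks × 7 / 365.25:

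- 25 mg: 40 × 12 × 7 / 365.25 = 9.2
- 50 mg: 80 × 12 × 7 / 365.25 = 18.4
- 400 mg: 90 × 288 × 7 / 365.25 = 496.8

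**3. What exposure adjustment does.** The SAP 7.4.1 rate (patients with a first event / time at risk) was simulated under a constant hazard of 20 per 100 patient-years. It returned about 20 for both 12-week and 288-week exposure, so length of exposure is handled. With a further hazard of 10 in the 288-week column it returned about 30. The period difference passes straight through.

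**4. Spurious ratio, 400 mg against 25/50 mg, with no drug effect.** Let b be the rate of other infections, c the COVID-19 rate during 400 mg time, and s the COVID-19 rate during 25/50 mg time as a fraction of c. Then

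ratio = (b + c) / (b + s·c).

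All three are assumptions. The ratios below are for c = 2 to 20 per 100 patient-years.

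| b per 100 patient-years | s = 0 | s = 0.5 | s = 1 |
|---|---|---|---|
| 10 | 1.20 to 3.00 | 1.09 to 1.50 | 1.00 |
| 20 | 1.10 to 2.00 | 1.05 to 1.33 | 1.00 |
| 40 | 1.05 to 1.50 | 1.02 to 1.20 | 1.00 |

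Example: b = 20, c = 10, s = 0 gives 30 / 20 = 1.50. If s exceeds 1, the ratio falls below 1. For severe infections with an assumed b = 1 and s = 0, c = 0.5, 1 and 2 give 1.5, 2.0 and 3.0.

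**5. Precision of the low-dose columns.** With zero events, the exact upper 95% limit is 3.69 / patient-years. That is 40.1 per 100 patient-years for 25 mg and 20.1 for 50 mg, even at maximum size. With 1 to 2 severe infections per 100 patient-years, the two columns together (9.2 + 18.4 = 27.6 patient-years) would expect about 0.3 to 0.6 events.

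**6. Effect of the change.** With COVID-19 terms removed, c = 0 and the ratio is b / b = 1.00 in this model.

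**The case against.** The case on the other side is substantial, and much of it stands.

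- **COVID-19 is not hidden at event level.** Adverse events are tabulated by SOC and preferred term, and SAP 7.4.1 computes the rate for each preferred term. A COVID-19 term would have its own row by dose. A reader might infer that the tables cannot separate COVID-19 from a drug effect. That holds only for aggregate rows, where a patient counts once across many terms.
- **10 December 2020 is an enrolment date, not the start of the pandemic.** The protocol treats COVID-19 as current two months earlier, and Part 1 entry as late as mid-September 2020 fits the SAP. Some 25/50 mg time may therefore be pandemic time.
- **The SAP recognises differing entry times.** It gives them as one reason for several sets, and three of the four listed sets do not mix the parts. But those three offer no cross-part dose comparison, and the set that does has no calendar rule.
- **The low-dose columns are small and nothing is tested** (Protocol 7.2). A severe-infection ratio of the sizes above could easily be lost in noise. The columns also differ in fed or fasted dosing and entry criteria.
- **Other routes exist.** Protocol 6.1 says the implications of visit deviations will be considered in the analysis. SAP 7.8.1 refers to a separate guideline and allows updates to its user-defined categories. Neither commits to a COVID-19 display.

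A reader might also infer that remote visits bias the comparison. Protocol 1.4 still requires new and ongoing adverse events to be assessed at them, and the documents support no direction of bias.

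**Conclusion.** The point stands for the aggregate rows of the combined dose-at-onset set: any TEAE, infections SOC, grade 3 or higher infections, and SAEs. The absence of calendar overlap between 25/50 mg and 400 mg follows from the SAP alone. That COVID-19 distorts the comparison is a possibility, not a certainty.

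With 20 other infections and 2 to 20 COVID-19 cases per 100 patient-years, the spurious ratio is 1.10 to 2.00 with no COVID-19 in low-dose time, 1.05 to 1.33 at half the later rate, and 1.00 at equal rates. Which applies cannot be settled without the first Part 1 entry date. The result also assumes that COVID-19 terms are coded to the infections SOC and that the rate formula is applied to aggregate rows as well as to preferred terms.

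A reader might go further and conclude that infection rates would rise with dose, or with time on drug within Part 1, even for an inert drug. Both conclusions need the missing entry date. Nor is this a type I error problem or a fault in the primary endpoint; the harm is misreading a descriptive table.

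**What to change.** In SAP 7.8.1, for the combined dose-at-onset set:

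1. Present the exposure-adjusted rates of all TEAEs, infections SOC, severe infections and SAEs twice, with and without COVID-19 preferred terms, and list those terms.
2. Footnote that the 25 and 50 mg columns share no calendar time with the 400 mg column. This also covers period differences that removing COVID-19 terms does not address.

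Optionally, add a 100, 200 and 400 mg version limited to events and time on or after 10 December 2020. It must say how patients whose first event came earlier are counted. It must also note that the 100/200 mg patients are then established responders while 400 mg patients are new entrants, possibly from placebo, and that investigator-chosen increases from 100 to 200 mg open at the same time. It is a sensitivity analysis, not a clean comparison, and its intervals will be wider.

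Two passages in SAP 6.1 should be reconciled in the same revision. One says all Part 1 patients had moved to 100 mg, while another keeps the 200 mg group on 200 mg. The text also refers to a fifth set when four are listed. Neither alters the finding for 25/50 mg.

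The cost is a few extra tables and a footnote from data already collected, with no change to trial conduct or the primary endpoint.

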Visit	1 ^{1, 2}	1.1 ³	1.2 ³	1.3 ³	2	2.1 ³	3	4	5	6	7	8	9	10	11	12	13	14
Week	(Day 1)	2	4	8	12	14	24	36	48	60	72	84	96	108	120	132	144	156
Visit window (days)		±7	±7	±7	±7	±3	±7	±7	±7	±7	±7	±7	±7	±7	±7	±7	±7	±7
Informed consent	X																	
Demographics	X																	
Medical history	X																	
Smoking/alcohol history	X																	
Baseline conditions	X																	
In-, ex-criteria	X																	
Concomitant therapy	X	X	X	X	X	X	X	X	X	X	Х	X	Х	X	X	X	X	Х
Body weight	\mathbf{x}^1								X				X				X	
Vital signs	x ¹	X	X	X	X		X	X	X	X	X	X	X	X	X	X	X	X
Physical examination	\mathbf{x}^1	X	X	X	X		X	X	X	X	X	X	X	X	X	X	X	X
Resting 12 lead ECG	\mathbf{x}^1								X				X				X	
Pregnancy testing ⁴	\mathbf{x}^1	X	X	X	X		X	X	X	X	X	X	X	X	X	X	X	X
Adverse Events	X	X	X	X	X	X	X	X	X	X	X	X	X	X	X	X	X	X
Contact IRT	X				X		X	X	X	X	X	X	X	X	X	X	X	X
Dispense study medication	X				X		X	X	X	x	X	X	x	X	X	X	X	X
Collect study medication					X		X	X	X	X	Х	X	Х	X	X	X	X	Х
PASI, sPGA	x ¹				X		X	X	X	X	Х	X	Х	X	X	X	X	Х
																	Ī	

Page 6 of 84

Trial Periods	Screening/ Double Blind Treatment							(Open La	abel Tro	eatment	t						
Visit	1 ^{1, 2}	1.1 ³	1.2 ³	1.3^{3}	2	2.1 ³	3	4	5	6	7	8	9	10	11	12	13	14
Week	(Day 1)	2	4	8	12	14	24	36	48	60	72	84	96	108	120	132	144	156
Visit window (days)		±7	±7	±7	±7	±3	±7	±7	±7	±7	±7	±7	±7	±7	±7	±7	±7	±7
Columbia-Suicide Severity Rating Scale (C-SSRS) ⁷	\mathbf{x}^1				X		X	X	X	X	X	X	х	x	х	X	х	X
Safety laboratory samples	x^2	X	X	X	X		X	X	X	X	X	X	X	X	X	X	X	X
Biomarker samples (serum)	\mathbf{x}^1								X				x					
Whole blood (PBMC) for flow cytometry (pre-dose) 8	\mathbf{x}^1								Х				х					
Termination of trial medication																		
Trial completion 10, 11																		
Vital status collection ¹³																		

Page 7 of 84

Trial Periods					Oper	Label T	[reatme	nt				Follow-Up	
Visit	15	16	17	18	19	20	21	22	23	24	EOT^{12}	EOO ¹¹	
Week	168	180	192	204	216	228	240	252	264	276	288	292	
Visit window (days)	±7	±7	±7	±7	±7	±7	±7	±7	±7	±7	±7	+7	
Informed consent													
Demographics													
Medical history													
Smoking/alcohol history													
Baseline conditions													
In-, ex-criteria													
Concomitant therapy	X	X	X	Х	X	X	X	Х	X	X	х	Х	
Body weight			X				X				X		
Vital signs	X	X	X	Х	X	X	X	Х	X	X	х	Х	
Physical examination	X	X	X	X	X	X	X	X	X	X	X		
Resting 12 lead ECG			X				X				Х		
Pregnancy testing ⁴	X	X	X	X	X	X	X	X	X	X	X	X	
Adverse Events	X	X	X	X	X	X	X	X	X	X	X	X	

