Contact IRT	X	X	Х	X	X	X	X	Х	X	X	Х		
Dispense study medication	X	X	X	Х	X	X	X	Х	X	X			
Collect study medication	X	X	X	Х	X	X	X	Х	X	X	х		
PASI, sPGA	X	X	X	X	X	X	X	X	X	X	X		
Columbia-Suicide Severity Rating Scale (C-SSRS) ⁷	X	x	x	x	x	x	x	x	x	x	x	X	
Safety laboratory samples	X	X	Х	X	X	X	X	X	X	X	X		
Biomarker samples (serum)											Х		
Whole blood (PBMC)													
for flow cytometry											X		
(pre-dose) ⁸													

Page 8 of 84

Trial Periods		Open Label Treatment										Follow-Up
Visit	15	16	17	18	19	20	21	22	23	24	EOT^{12}	\mathbf{EOO}^{11}
Week	168	180	192	204	216	228	240	252	264	276	288	292
Visit window (days)	±7	±7	±7	±7	±7	±7	±7	±7	±7	±7	±7	+7
Termination of trial medication											X	
Trial completion ^{10, 11}												X
Vital status collection ¹³												X

Boehringer Ingelheim 06 Oct 2020

Clinical Trial Protocol Page 9 of 84

Proprietary confidential information © 2020 Boehringer Ingelheim International GmbH or one or more of its affiliated companies

Flow Chart Footnotes:

Visit 1 will occur on the same day as End of Treatment (EOT) Visit in 1407-0030. Weight, vital signs, physical exam, ECG, pregnancy test, PASI, sPGA,

, C-SSRS, biomarker samples, whole blood

(PBMC) for flow cytometry and are performed only once on that day as part of the EOT Visit in 1407-0030. Visit 1 may be delayed up to 16 weeks if necessary for administrative reasons. If Visit 1 is delayed, these procedures will be done at Visit 1, except for PK, Biomarker and flow cytometry samples.

² Safety laboratory samples will be taken twice in the same day as part of both the EOT Visit in 1407-0030 and for Visit 1 in 1407-0005. Visit 1 collection is only for the following laboratory tests that are not assessed at EOT in study 1407-0030: infection testing, glycosylated Hbc, LDL-cholesterol/HDL-cholesterol, cholesterol total, and triglycerides. If Visit 1 is delayed, then a sample will be taken at Visit 1 to include all tests included in the two samples and only one sample will be taken at EOT for 1407-0030.

³For patients entering from Part 1 of trial 1407-0030, Visit 2.1 is a phone visit, with only adverse events and concomitant medication collected. Visits 1.1, 1.2 and 1.3 do not apply. For patients entering from Part 2 of trial 1407-0030, Visits 1.1, 1.2 and 1.3 to be performed at the clinic with all procedures indicated, Visit 2.1 does not apply.

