5.2.3 Safety laboratory parameters

Safety laboratory parameters to be assessed are listed in Table 5.2.3: 1. For the sampling time points please see the Flow Chart.

All analyses will be performed by a central laboratory, the respective reference ranges will be provided in the ISF.

Blood samples for safety will be drawn prior to drug administration, under fasted conditions.

Instructions regarding sample collection, sample handling/processing and sample shipping are provided in the Laboratory Manual in the ISF.

The central laboratory will send reports to the investigator. It is the responsibility of the investigator to evaluate the laboratory reports. Clinically relevant abnormal findings as judged by the investigator will be reported as adverse events (please refer to Section 5.2.6).

In case the criteria for hepatic injury are fulfilled, a number of additional measures will be performed (please see Section 5.2.6.1 and the DILI Checklist provided in the ISF or

Page 43 of 84

Electronic Data Capture (eDC) system). The amount of blood taken from the patient concerned will be increased due to this additional sampling.

The central laboratory will transfer the results of the analysis to the sponsor.

Table 5.2.3: 1 Safety laboratory tests

Category	Test name
Haematology	Hematocrit (Hct)
	Hemoglobin (Hb)
	Glycosylated Hbc (HbA1c) ¹
	Red Blood Cell Count/ Erythrocytes
	Reticulocyte Count
	White Blood Cells / Leucocytes
	Platelet Count/ Thrombocytes
Diff. Automatic	Neutrophils (relative and absolute count)
	Eosinophils (relative and absolute count)
	Basophils (relative and absolute count)
	Monocytes (relative and absolute count)
	Lymphocytes (relative and absolute count)
Diff. Manual (if Diff Automatic is abnormal)	Neutrophils, bands (Stabs)
,	Neutrophils, polymorphonuclear (PMN)
	Eosinophils
	Basophils
	Monocytes
	Lymphocytes
Coagulation	Activated Partial Thromboplastin Time (aPTT)
	Prothrombin time (INR)
	Fibrinogen
Enzymes	AST(GOT)
•	ALT(GPT)
	Alkaline Phosphatase (AP)
	Creatine Kinase (CK)
	CK-MB, only if CK is elevated
	Gamma-Glutamyl Transferase (GGT/γ-GT)
	Lactic Dehydrogenase (LDH)
	Lipase
	Amylase
Electrolytes	Calcium
•	Sodium
	Potassium
	Chloride
	Bicarbonate

Only at Visit 1, Visit 5, Visit 9, Visit 13, Visit 17, Visit 21 and EOT Visit

Page 44 of 84

Table 5.2.3: 1 Safety laboratory tests Cont'd

Category	Test name
Substrates	Glucose
	BUN
	Uric acid
	Creatinine
	eGFR (estimated by CKD-EPI formula)
	Bilirubin Total

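### The combined by-dose TEAE table mixes unequal adverse-event enquiry in Weeks 0-12 (four contacts on 400 mg, one on 25-200 mg), and no planned table compares the doses under an equal schedule

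*SAP*

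**What the plan says.** **Schedule.** The protocol flow chart marks adverse events, vital signs, physical examination and safety laboratory at Visits 1.1, 1.2 and 1.3 (Weeks 2, 4 and 8). Footnote 3 splits these by origin. For Part 1 patients (blinded placebo to 200 mg), "Visits 1.1, 1.2 and 1.3 do not apply". The other half reads: "For patients entering from Part 2 of trial 1407-0030, Visits 1.1, 1.2 and 1.3 to be performed at the clinic with all procedures indicated". All Part 2 patients receive open-label 400 mg from Visit 1. Part 1 alone has a telephone call at Week 14, covering only adverse events and concomitant medication. From Week 24 both parts follow the same 12-weekly visits.

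**Findings become events.** Protocol 5.2.3 on laboratory results: "Clinically relevant abnormal findings as judged by the investigator will be reported as adverse events". Protocol 5.2.6.1.1 treats vital signs, ECG and examination changes in the same way.

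**Analysis.** The primary analysis is the exposure-adjusted TEAE rate (SAP 7.4.1). SAP 6.1 lists four adverse-event sets. The last combines both parts: "part 1 and part 2 combined) where events are classified under the treatment at onset in 1407-0005 with treatment columns" for the five active doses. Exposure-adjusted rates are specified for the set classified by dose at onset, because exposure lengths vary. The text calls that set the fifth, but the description identifies it. For Part 2, "adverse events will only be summarized for the entire treatment period and will not be summarized for the first 12 weeks", nor for the time after Week 12. The reason given is that Part 2 has no scheduled titration. Laboratory, vital-sign and suicidality summaries for both parts combined are nevertheless split at Week 12.

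**The concern.** Dividing by time at risk corrects for how long patients were followed. It does not correct for how often they were asked or examined. The 400 mg column contains a densely observed first 12 weeks. The 25 and 50 mg columns consist only of a sparsely observed one, because those patients move to 100 mg at Week 12. SAP 6.1 names dose, titration and time of entry as reasons for separate sets but not the visit schedule.

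The table affected carries the primary endpoint, and the column affected is the anticipated therapeutic dose (Protocol 3.1). Moderate nausea or vomiting is part of an adverse event of special interest (Protocol 5.2.6.1.4), and non-serious symptoms of that kind are the ones most open to loss between visits. A reader comparing 400 mg with lower doses would have no planned adverse-event table in which enquiry is equal.

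**Working it through.** The documents give no figure on this point, so there is none to reproduce. The steps below count contacts and then apply the SAP rate with the same true event rate at every dose.

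**1. Contacts (flow chart, footnote 3).** Post-dose adverse-event contacts, 400 mg against Part 1:
- Weeks 0-12: 4 (Weeks 2, 4, 8, 12) against 1 (Week 12)
- Weeks 0-24: 5 against 3
- Weeks 0-48: 7 against 5

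**2. Mean wait from event to next contact, Weeks 0-12.** For intervals of length L this is Σ(L²/2)/12.
- 400 mg: (2 + 2 + 8 + 8)/12 = 1.7 weeks
- Part 1: 72/12 = 6.0 weeks

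**3. Share of events recorded.** *Assumption, not in the documents:* the chance that an event is reported halves for every h weeks until the next contact. Over an interval L the mean is c(L) = h/(L ln 2) × (1 − 2^(−L/h)). For h = 12, c(2) = 0.944, c(4) = 0.893 and c(12) = 0.721.
- 400 mg, Weeks 0-12: (4 × 0.944 + 8 × 0.893)/12 = 0.910
- Part 1, Weeks 0-12: 0.721
- Part 1, Weeks 12-24 (intervals 2 and 10 weeks): 0.790; 400 mg: 0.721

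**4. Effect on the tabulated rate.** The SAP rate is first events divided by time to first event or censoring. With true rate λ and wait w(t), the recorded hazard is λ·2^(−w(t)/h), with cumulative value M(t). The rate is (1 − e^(−M(T))) / ∫₀ᵀ e^(−M(t))dt. The comparison is 400 mg against patients on 100 or 200 mg throughout, at equal follow-up T.

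Hand check for a rare event, h = 12, T = 48: (12 × 0.910 + 36 × 0.721) / (12 × 0.721 + 12 × 0.790 + 24 × 0.721) = 36.88/35.44 = 1.04.

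| λ per year | T (weeks) | h = 12 | h = 26 | h = 52 | full recall |
|---|---|---|---|---|---|
| 0.1 | 48 | 1.04 | 1.02 | 1.01 | 1.00 |
| 1 | 48 | 1.06 | 1.03 | 1.01 | 1.00 |
| 3 | 48 | 1.10 | 1.05 | 1.03 | 1.00 |
| 0.1 | 288 | 1.01 | 1.00 | 1.00 | 1.00 |
| 1 | 288 | 1.03 | 1.02 | 1.01 | 1.00 |
| 3 | 288 | 1.09 | 1.05 | 1.02 | 1.00 |

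The rate 0.1 stands for a single preferred term, the level at which SAP 7.4.1 defines time at risk. Rates of 1 to 3 stand for any TEAE. All three are assumptions. A recall half-life as short as 4 weeks would raise the top values to 1.24 (48 weeks) and 1.17 (288 weeks).

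**5. Against the 25 and 50 mg columns (Weeks 0-12 only), T = 48.** With h from 12 to 52 the ratio is 1.015 to 1.139 if all patients share one rate. If patients differ (gamma frailty, variance 1, so that e^(−M) becomes 1/(1 + M)), it is 0.735 to 1.040. With full recall and the same frailty it is 0.71 to 0.97. The 400 mg rate is then averaged over longer, lower-risk time, which can outweigh the ascertainment effect.

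**6. Which common period.** With onset and time at risk starting at Week 12, the Week 14 call falls inside the window and the ratio against 100/200 mg is 0.94 to 0.99 at 48 weeks (same h and λ). Starting at Week 24 gives 1.00.

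**The case against.** Adverse events are collected continuously from consent (Protocol 5.2.6.2.1), onset dates are mandatory (8.3.1) and extra monitoring visits are allowed (6.1), so an event between visits is still reportable at Week 12. The recall half-lives have no source in the documents. The additional Part 2 visits are a deliberate safety measure. No hypothesis is tested (7.2), and Protocol 3.2 concedes that no controlled analysis is possible. The parts also differ in entry criterion, time in the preceding trial, blinding and fed or fasted dosing, so an equal schedule would not by itself make the comparison fair.

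Much of this stands. It keeps the effect modest and conditional, and it rules out three stronger readings that a reader might infer.

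- *First-12-week rates are set side by side across the parts.* They are not. The SAP rules out a first-12-week adverse-event summary for Part 2, so ratios confined to that window (0.910/0.721 = 1.26 at h = 12) describe no planned output.
- *400 mg will look worse even with no drug difference.* That requires incomplete recall or findings seen only at visits. The documents establish neither the extent of these nor, against 25 and 50 mg, the direction.
- *Only a later-period table should be used to compare doses.* That would hide early 400 mg events and drop patients who stopped early.

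The objection does not show that the table is free of the difference, that exposure adjustment removes it, or that the SAP has considered it. Descriptive rates are this trial's primary output and are meant to support registration submissions (Protocol 1.3).

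**Conclusion.** The point holds in a limited form. The contact imbalance in Weeks 0-12 is exact, it enters the combined exposure-adjusted TEAE set, and no planned adverse-event table avoids it. Under recall half-lives of 12 to 52 weeks, the whole-treatment 400 mg rate is raised by about 1% to 10% at 48 weeks and 0% to 9% at 288 weeks against patients on 100 or 200 mg throughout. With full recall it is not raised at all. Against 25 and 50 mg no direction can be stated.

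Two limits apply. The range covers recall loss only; the documents do not say how many TEAEs would come to light only through an examination or laboratory test, which depends on the number of clinic visits (7 against 4 by Week 48; 27 against 24 by Week 288). The 100 mg column also holds patients who moved up from lower doses at Week 12, so its actual mix will differ from the comparison above.

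The matter is worth correcting in the SAP. It does not invalidate the primary analysis.

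**What to change.** In SAP 6.1:

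1. Remove the bar on period-specific adverse-event summaries for Part 2. Add one supportive exposure-adjusted TEAE set with Part 2 400 mg beside the Part 1 open-label columns. Start both onset and time at risk at Week 24. If Week 12 is preferred, footnote that the Part 1-only Week 14 call biases slightly the other way.
2. Keep the Day 1 combined set as the main display. Footnote the four-against-one contacts in Weeks 0-12.
3. In the same footnote, report the exclusion of Part 1 patients who stop before Week 12, which has no Part 2 counterpart. The SAP applies it to the second and fourth sets; the combined set is fourth as listed but is then called the fifth, so state plainly whether it applies.
4. Add a Weeks 0-12 column for 400 mg, and state that early cross-dose differences will be read mainly from deaths and SAEs. Discontinuations due to adverse events are less suitable, since an extra visit with tests can itself prompt one.

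The cost is SAP wording and further runs of existing table programs, with no new data or visits. The downside is that the supportive set omits early 400 mg events and early discontinuations, so it supplements the combined set and does not replace it.
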